3.6.3 Summaries of Baseline Characteristics, Demographics, and Other Analyses

Demographic and Baseline Characteristics

The number and percentage of participants screened, randomized, the primary reasons for screening failure, and the primary reason for discontinuation will be displayed.

Demographic variables (including age, gender, weight, and height), baseline characteristics, primary and comorbid conditions, and prior and concomitant therapies will be summarized either by descriptive statistics or categorical tables.

3.7 Interim Analyses

All efficacy analyses will be performed based on the data up to Week 24 when all the randomized participants have completed Week 24 or discontinued prior to Week 24. Safety analysis will include all available data up to the cutoff date for the interim database lock. Regardless of the result of the interim analysis (safety and efficacy), the study will continue as planned. Double blinding only to treatment assignment will be maintained at all investigational sites after all participants have completed Week 24. The results of interim analyses (safety and efficacy) will not be shared with the investigators prior to the completion of the study. The study will continue as double-blind only after Week 24 acknowledging that the sponsor will be unblinded at that point in order to analyze and report the data. The study team responsible for the ongoing monitoring of the study will remain blinded to the treatment-level results of this interim analysis (safety and efficacy).

3.8 Multiplicity

No multiplicity adjustment is planned in this trial.

3.9 Sample Size and Power Calculations

A total of 160 participants will be enrolled. Assuming a discontinuation rate of approximately 47%, 84 participants are expected to complete 52 weeks of treatment. The discontinuation rate was estimated from previous study (Protocol 012), which was a 12 week study.

The probability of observing at least one AE in this study depends on the number of participants treated and the underlying incidence with an AE in the study population. If the underlying incidence of an AE is 2%, the probability of observing at least one AE is 82% among 84 participants and 57% among 42 participants. If no participants had a specific AE, then the upper bound of the 95% CI of the underlying incidence rate would be 4.3% for 84 participants and 8.4% for 42 participants. For LCQ total score, assuming a 3.7 change from baseline and a SD of 3.9 at Week 12 based on Protocol 012, a 95% confidence interval of change from baseline in LCQ total score would be (2.9, 4.5) for 84 participants and (2.5, 4.9) for 42 participants.

3.10 Subgroup Analyses and Effect of Baseline Factors

No subgroup analysis is planned in this study.

3.11 Compliance (Medication Adherence)

For each participant, percent compliance will be calculated using the following formula:

$$\text{Percent Compliance} = \frac{\text{Number of Days on Therapy}}{\text{Number of Days Should Be on Therapy}} \times 100\%$$

A day within the study will be considered an “On-Therapy” day if the participant takes all required medication as instructed in Section 8 of the Protocol – Study Assessments and Procedures. When a participant takes less than or more than the required medication on a day, that day is not considered an On-Therapy day.

For participants who are followed for the entire study period, the “Number of Days Should Be on Therapy” is the total number of days from the first scheduled treatment day to the last scheduled treatment day. For participants who discontinue from the study medication permanently, the “Number of Days Should Be on Therapy” is the total number of days from the first scheduled treatment day to the last dose day.

Summary statistics will be provided on percent compliance for the APaT population.

3.12 Extent of Exposure

The duration of treatment for each participant will be evaluated by calculating the number of days on therapy. Exposure to study medication will be summarized using descriptive statistics (mean, SD, median, minimum, and maximum) for the APaT population.

Appendix: Relative day ranges

Since it is not always possible for all study participants to come in for their clinic visits on the exact day specified in the protocol schedule, the following relative day ranges will be defined for each time point.

	Scheduled day	LCQ, CSD, vital signs	EQ5D-5L, PGIC, laboratory parameters	Body weight
Baseline	1	Day \leq 1	Day \leq 1	Day \leq 1
Week 4	28	2 \leq Day \leq 41	--	2 \leq Day \leq 55
Week 8	56	42 \leq Day \leq 69	--	--
Week 12	84	70 \leq Day \leq 125	2 \leq Day \leq 125	56 \leq Day \leq 125
Week 24	168	126 \leq Day \leq 216	126 \leq Day \leq 266	126 \leq Day \leq 266
Week 38	266	217 \leq Day \leq 315	--	--
Week 52	365	316 \leq Day	267 \leq Day	267 \leq Day

For the analysis of safety parameters, Day at post-baseline timepoints must be \leq 14 days following the last dose.
The analysis week for CSD will be defined based on the day of study visit by subjects. Seven (7) days to 1 day before the study visit will be used as the measurements for the analysis week to which the study visit day belongs.

If a subject has data on multiple days within a day range, the measurement closest to the scheduled day within the day range will be used in the analysis. If there are observations before and after the scheduled day that are equally apart from the scheduled day, then the observation after the scheduled day will be used for analysis. If two or more measurements are obtained on the same day, the average will be used as the observation for the day.

Baseline variable is defined as the last non-missing value prior to treatment. Typically this is the measurement taken at Visit 1 or Visit 2, depending on the endpoint.

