8.3.6 Clinical Safety Laboratory Assessments

- Refer to Appendix 2 for the list of clinical laboratory tests to be performed and to the SoA for the timing and frequency.
- The investigator must review the laboratory report, document this review, and record any clinically relevant changes occurring during the study in the AE section of the case report form (CRF). The laboratory reports must be filed with the source documents. Clinically significant abnormal laboratory findings are those which are not associated with the underlying disease, unless judged by the investigator to be more severe than expected for the participant's condition.
- All protocol-required laboratory assessments, as defined in Appendix 2, must be conducted in accordance with the laboratory manual and the SoA.
- If laboratory values from nonprotocol specified laboratory assessments performed at the institution's local laboratory require a change in study participant management or are considered clinically significant by the investigator (eg, SAE or AE or dose modification), then the results must be recorded in the appropriate CRF (eg, SLAB).
- For any laboratory tests with values considered clinically significantly abnormal during participation in the study or within 14 days after the last dose of study intervention, every attempt should be made to perform repeat assessments until the values return to normal or baseline or if a new baseline is established as determined by the investigator.

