8.3.7 Renal and Urological Safety Procedures

Safety assessments will be performed in all participants in order to monitor renal and urological safety during the course of the study. Participants will be monitored for hematuria using urinary dipstick (performed at the study site) and urinary crystals through urinalysis (performed at the central laboratory). Dipstick and urinalyses (including microscopy performed at the central laboratory) will be collected as outlined in the SoA.

If during screening, a participant has crystalluria and/or unexplained hematuria (defined as participants without a history of recent menses, urinary tract infection, or recent procedure/instrumentation that would explain the hematuria), the investigator should:

- Review and confirm if the finding is a new finding or a previously documented finding.
- Evaluate the participant's medical history to identify conditions (ie, prior renal disease, prior history of kidney stones, medications, gastrointestinal conditions) and make a clinical determination if the participant is at high or low risk of potential complications/worsening due to an associated renal/urinary condition or its treatment, or requires a change in therapy for that condition that may interfere with interpretation of safety data collected during the study.

- If high risk, the participant should not be enrolled and should be considered for further evaluation.
- If low risk, the participant may continue with screening.

If after randomization, the participant has confirmed, unexplained hematuria and/or urinary crystals, an urine sample collected via a specialized filter will be shipped to Sponsor or designee and assessed for the presence of MK-7264 urinary crystals via Raman spectroscopy. Raman spectroscopy is sensitive to the chemical structure of the molecule and MK-7264 has unique chemical structure compared to common urinary crystals. See vendor's site manual for further procedural details.

If a participant has confirmed MK-7264 urinary crystals, the Sponsor will inform the investigator and require discontinuation of the participant from study intervention with the recommendation to follow-up at approximately 2-week intervals with additional specialized urine analysis performed until resolution of MK-7264 urinary crystals.

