8.10.5 Discontinued Participants Continuing to be Monitored in the Study

If a participant is discontinued from the study intervention early, the Discontinuation Visit assessments are to be performed as soon as possible.

It is intended that all participants should be followed through completion of the study, regardless of premature discontinuation of intervention unless the participant withdraws consent. Thus, participants who discontinue from study intervention prior to completion of the study should continue to be monitored to obtain relevant information through the end of the study. Study site visits/telephone calls should be made at timepoints that correspond to each remaining study visit. The follow-up information, limited to AEs, concomitant medication use, and patient report outcomes (site visits only) will be collected as outlined in the SoA.

Concomitant therapies specifically prohibited (see Section 6.5) while the participant was on study intervention are no longer prohibited after discontinuation of study intervention.

For these participants who have discontinued study intervention early, sites will be instructed to exert diligent efforts to continue to contact them. To enable sites to reach participants, the participants should provide primary and secondary contact information (eg, home telephone, work telephone, mobile telephone). Sites must document the outcome of the telephone contact(s), to demonstrate diligent efforts have been made. If a participant does not agree to be contacted for follow-up for each of the remaining visits (as described in Section 7.1), the participant should be encouraged to accept a telephone contact at least at Visit 8 date.

Additionally, the ICF will explain the importance of continued data collection from participants, including the use of continued contact by telephone.

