3.0 ANALYTICAL AND METHODOLOGICAL DETAILS

3.1 Statistical Analysis Plan Summary

Key elements of the statistical analysis plan are summarized below; the comprehensive plan is provided in Sections 3.2-3.12.

Study Design Overview	Phase 3 study, Randomized, Double-blind Clinical Study to Evaluate the Long-term Safety and Efficacy of MK-7264 in Japanese Adult Participants with Refractory or Unexplained Chronic Cough
Treatment Assignment	Participants will be randomized in a 1:1 ratio to either MK-7264 45 mg BID or MK-7264 15 mg BID.
Analysis Populations	Efficacy: Full Analysis Set (FAS) population. Safety: All Participants as Treated (APaT) population.
Primary Endpoint	
• Adverse events (AEs)• Study treatment discontinuations due to AE
Statistical Methods for Key Efficacy Analyses	Change from baseline in LCQ total score at Week 12 and through Week 52 will be analyzed using the longitudinal analysis of covariance (ANCOVA) model. The model will include terms for treatment, visit, the interactions of treatment by visit, and baseline value as covariates. The change from baseline to each visit and 95% CIs will be estimated from this model.
Statistical Methods for Key Safety Analyses	AEs will be summarized by the number and percentage of the participants who experienced respective events. Change from baseline in laboratory tests, vital signs at respective timepoints will be summarized by descriptive statistics.
Interim Analyses	The planned interim efficacy analysis will be performed based on the data up to Week 24 when all the randomized participants have completed Week 24 or discontinued prior to Week 24. Safety analysis will include all available data up to the cutoff date for the interim database lock.
Multiplicity	No multiplicity adjustment is planned in this trial.
Sample Size and Power	A total of 160 participants will be enrolled. Assuming a discontinuation rate of approximately 47% at Week 52, 84 participants are expected to complete 52 weeks of treatment.

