3.6.2 Statistical Methods for Safety Analyses

Safety and tolerability will be assessed by clinical review of all relevant parameters including AEs, study treatment discontinuations due to AE, laboratory tests, vital signs measurements.

All safety analyses will be based on the APaT population.

AEs and other safety events will be summarized using the number and percentage of the participants who experienced respective events. The AEs observed up to 14 days after the last dose will be included in the analysis.

Taste-related AEs (including dysgeusia, ageusia, and hypogeusia, as well as other related terms) and oral paraesthesia/hypoesthesia are considered as AEs of interest.

Continuous measures such as changes from baseline in laboratory, vital signs parameters will be summarized using descriptive statistics.

Summary statistics for baseline, on treatment, and change from baseline values will be provided in table format.

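### Do the laboratory visit windows lose the discontinuation results that a long-term safety study needs?

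*Combined protocol and SAP*

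**What the plan says.** The Schedule of Activities (protocol Section 1.3) places hematology and chemistry at Visit 1, Visit 5 (Day 84 ±4), Visit 6 (Day 168 ±7), Visit 8 (Day 365 ±14) and the discontinuation visit. On that visit, protocol Section 8.10.5 says: "If a participant is discontinued from the study intervention early, the Discontinuation Visit assessments are to be performed as soon as possible". Follow-up after that point is "limited to AEs, concomitant medication use, and patient report outcomes (site visits only) will be collected as outlined in the SoA", so the discontinuation sample is the last scheduled laboratory test for someone who stops early.

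The sSAP Appendix assigns laboratory results to Week 12 (Days 2-125), Week 24 (Days 126-266) or Week 52 (Day 267 onward). Within a window, "the measurement closest to the scheduled day within the day range will be used in the analysis", and a tie goes to the later value. Safety values must lie within 14 days of the last dose.

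sSAP Section 3.1 describes the analysis: "Change from baseline in laboratory tests, vital signs at respective timepoints will be summarized by descriptive statistics". Section 3.6.2 adds: "Summary statistics for baseline, on treatment, and change from baseline values will be provided in table format". It does not define the on-treatment value. No last-value, worst-value or shift table is named.

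**The concern.** Two features pull against each other. The discontinuation sample is the participant's last scheduled laboratory observation, taken when a drug effect might have prompted stopping. The closest-value rule favours the earlier scheduled sample, because that one was taken near its target day. Someone sampled on Day 84 who stops and is sampled again on Day 110 appears in the Week 12 column with the Day 84 value only.

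If many participants were affected, the laboratory tables could under-represent numeric change at the end of exposure, for example in creatinine, eGFR or a single transaminase. The plan expects about 47% to discontinue, so the group at issue is not obviously small.

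A related worry is labelling. A discontinuation sample with no scheduled competitor is kept under the nominal week, so a Day 267 result is shown as Week 52.

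**Working it through.** **Plan's own figure.** sSAP Section 3.9 gives 160 enrolled, about 47% discontinuing and 84 completing. 160 × (1 − 0.47) = 84.8, which agrees with 84 to rounding (84/160 implies 47.5% discontinuing). Expected discontinuations: 160 − 84 = 76.

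**Does the rule displace the later sample?** Apply the closest-day and tie rules to every in-window visit day paired with every later discontinuation day in the span.

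- Visit 5 on Days 80-88, discontinuation after Day 84 and up to Day 125: 359 pairs. The discontinuation value wins 10 and loses 349 (97%). It never wins after Day 88.
- Visit 6 on Days 161-175, discontinuation after Day 168 and up to Day 266: 1442 pairs. It wins 28 and loses 1414 (98%). It never wins after Day 175.

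The mechanism is real. The spans are 125 − 84 = 41 days and 266 − 168 = 98 days, together 139 of 364 treatment days.

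**How many participants?** The documents give no stopping times, and the 47% comes from a 12-week study, so timing has to be assumed. Assume also that all 76 have a laboratory sample on the stopping day and that those stopping after Day 84 or 168 had a usable Visit 5 or 6 sample.

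| Assumed stopping pattern | Calculation | Displaced | Share of 160 |
|---|---|---|---|
| All by Day 84 | none in the spans | 0 | 0% |
| 90% by Day 84, rest uniform | 7.6 × 139/280 | 3.8 | 2.4% |
| Three quarters by Day 84, rest uniform | 19 × 139/280 | 9.4 | 5.9% |
| Half by Day 84, rest uniform | 38 × 139/280 | 18.9 | 11.8% |
| Constant hazard, S(d) = exp(−0.644 d/364) | 160[S(84) − S(125)] + 160[S(168) − S(266)] = 9.7 + 18.9 | 28.6 | 17.9% |
| Uniform over 364 days | 76 × 139/364 | 29.0 | 18.1% |
| None by Day 84, then uniform | 76 × 139/280 | 37.7 | 23.6% |

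If the sample comes 14 days after stopping, the spans shrink to 27 + 84 = 111 days. The three-quarters and uniform patterns then give 19 × 111/280 = 7.5 and 76 × 111/364 = 23.2. Missed Visit 5 or 6 samples, or missed discontinuation samples, lower every count.

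**Labelling.** A kept discontinuation sample can be shown up to 365 − 267 = 98 days early as Week 52, or up to 84 − 2 = 82 days early as Week 12. Samples on Days 267-350 would form 5.7/90.7 = 6.3% (three-quarters pattern) to 17.5/104.5 = 16.8% (uniform) of the Week 52 column. The denominators are 84 completers plus all who stop from Day 267.

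**Where else do these results go?**

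- The primary endpoints are adverse events and treatment discontinuations due to them. sSAP Section 3.6.2 counts adverse events up to 14 days after the last dose and does not window them.
- Protocol Section 8.3.6 requires the investigator to review each report and to "record any clinically relevant changes occurring during the study in the AE section". The definition in Section 10.3.1 also takes in abnormal results that have worsened since baseline.
- The hepatic event of clinical interest in Section 8.4.7 applies to any protocol-specified or unscheduled test.
- Confirmed drug crystals have their own path in Section 8.3.7, with "additional specialized urine analysis performed until resolution of MK-7264 urinary crystals".

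What the by-visit table omits is therefore mainly numeric movement that met none of these criteria, in people who already contribute a value to the same window.

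**The case for a change.** The best argument for a change is that the study exists to describe long-term safety, and laboratory tests are a listed safety endpoint. Exclusion criterion 7 admits participants with eGFR from 30 to below 50 if renal function is stable, so sub-clinical renal drift is of interest. The Week 24 analysis supports a regulatory filing and uses the same windows. Against that, one sentence and one table of last on-treatment values cost almost nothing.

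Part of this stands. The on-treatment value is undefined, no named table clearly recovers the displaced results, and readers of the by-visit table should know that some values come from discontinuation visits.

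The rest is weaker. Letting the discontinuation value replace the scheduled one would mix exposure times within a column, and the argument does not ask for that. A last-value table has its own flaw. For significant abnormalities Section 8.3.6 says "every attempt should be made to perform repeat assessments until the values return to normal or baseline", or until a new baseline is established. For the participants of most interest, the last value within 14 days may be the recovered one. A sample taken late in that period is also hardly on-drug: with the 7-10 hour half-life in protocol Section 4.3.3, 14 days is at least 336/10 = 33.6 half-lives. The documents do not show that the displaced values would shift the laboratory profile in a particular direction.

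**Conclusion.** The description is accurate, but it is not a defect. The windows do what by-visit windows are for: they show each participant near the nominal time, one value per column. No passage contradicts another and no stated figure is wrong. The displaced results remain in the database, and those that matter clinically enter the adverse event or clinical-interest data without passing through the windows.

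The undefined on-treatment summary is a gap that analysts can fill when they specify the tables. The sSAP Appendix already limits safety values to 14 days after the last dose, and the natural reading is all post-baseline values within that limit. Handling of repeat tests and a count of discontinuation-visit values in each column can be settled at the same stage. These are presentation choices, and the plan gives sound results without amendment.

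The affected number is 0 to about 38 of 160 across the stopping patterns examined, and about 9 to 29 for the three-quarters, half, constant-hazard and uniform patterns. All these counts rest on assumed stopping times and on complete sampling at discontinuation and at Visits 5 and 6. None touches a primary endpoint.
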